4 CONFIDENTIALITY AND ETHICAL CONSIDERATIONS

Patient confidentiality will be maintained throughout the study. Patient records on the database are anonymous. Patient identifying details are replaced by codes, which cannot be broken by the researchers. There is no need to collect any additional data directly from patients currently. Therefore, no informed consent is required.

5 STUDY TIMELINES

The interim study reports will be submitted annually in December, 2010 to 2014. The final study report will be submitted in December 2016 at the latest. It is estimated that the LabRx database may not provide sufficient statistical power until 2014 for any event of interest to rule out a

hazard ratio of 1.5. However, the sponsor will check the number of incident of digitalis intoxication and rhabdomyolysis /myopathy, the number of potential study participants, patients who received prescriptions of dronedarone and digoxin (or statins), and statistical power based on the above identified number of events and dronedarone users each year. Provided that 336 or more events are captured for any outcome(s) of interest before 2014 which will be sufficient to rule out at least a hazard ratio of 1.5, the final data analysis and study report for the particular outcome(s) will be initiated immediately.

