3.3 EXPOSURE MEASUREMENT

Exposure will be defined as on-drug treatment or off-drug treatment. To identify exposure, all prescriptions for digoxin (or statins), dronedarone, and amiodarone will be identified and treatment episodes calculated. Statins of interest include atorvastatin, simvastatin, lovastatin, and pravastatin. Fluvastatin and rosuvastatin will not be considered for the potential interaction with dronedarone because they are not metabolized or only weakly metabolized by CYP3A4 and are not P-gp substrates.

Exposure will be categorized into the following three groups: 1) concomitant use of digoxin (or statins) and dronedarone, 2) concomitant use of digoxin (or statins) and amiodarone, and 3) digoxin (or statins) alone as the reference group, i.e. digoxin (or statins) without concomitant use of either dronedarone or amiodarone. The concomitant use of digoxin (or statins) and dronedarone (or amiodarone) will be defined as the treatment period during which a patient is on both of the drugs. Digoxin (or statins) alone will be defined as the treatment period during which a patient is on digoxin (or statins), but not on dronedarone or amiodarone. Amiodarone is included as part of exposure of interest because it is one of the major drugs that are identified to have potent interactions with digoxin (or statins) as a multi-channel blocker displaying antiarrhythmic properties of all four Vaughan-William's classes.

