3.6 SAMPLE SIZE

We calculated sample size based on the likelihood ratio test in the context of a Cox proportional hazards regression analysis. The preliminary analysis of the last five-year data in the LabRx suggested that there might be about 44,000 participants for the cohort of digoxins and about 86,000 participants for the cohort of statins during the next 5-year cohort accrual period (07/2009-06/2014). With these figures, the study would be able to rule out a hazard ratio of 1.42 for the outcome of digitalis intoxication, and a hazard ratio of 1.61 for the outcome of rhabdomyolysis and myopathy with the assumptions of 0.05 alpha level (type I error), 80% statistical power (type II error), 17.1% prevalence of dronedarone use in the study population (the sponsor's prediction), 1.1% baseline incidence rate for the outcome of digitalis intoxication⁹, and 0.3% baseline incidence rate for the outcome of rhabdomyolysis and myopathy¹⁰⁻¹¹. For a 4-year cohort accrual period (07/2009-06/2013), we estimate that the study would be able to rule out a hazard ratio of 1.51 with over 32,000 participants for the outcome of digitalis intoxication, and a hazard ratio of 1.69 with over 70,000 participants for the outcome of rhabdomyolysis and myopathy with the same assumption. For a 3-year cohort accrual period (07/2009-06/2012), we estimate that the study would be able to rule out a hazard ratio of 1.59 with over 25,000 participants for the outcome of digitalis intoxication, and a hazard ratio of 1.77 with over 58,000 participants for the outcome of rhabdomyolysis and myopathy with the same assumption (see [Table 3](#)).

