7 TABLES AND FIGURES

Table 1 Distribution of gender, age, and region of patients in the LabRx as of 2008 and in the US general population in 2005

Attributes	LabRx	US Population (2005)*
Male	50%	49%
US Region	Total Lives (%)	Total Lives (%)
Northeast	22%	19%
North Central	30%	22%
South	30%	36%
West	18%	23%
Age Group	Total Lives (%)	Total Lives (%)
00-20	28%	27%
21-39	32%	29%
40-64	34%	32%
65+	6%	12%

*Statistical abstract, US Census

Table 2 Age distribution in AF/AFL Patients in the LabRx (1/1985-3/2008)

Age (yrs)	N	%
18-29	3,705	1.5
30-49	36,089	14.2
50-64	86,431	34.1
>65	127,516	50.3
Total	253,741	100.0

Table 3 Estimated sample size

Outcome	Incidence in literature	Size of cohort*		Hazard Ratio
Digitalis intoxication	1.1% ⁹	3 years	25,000	1.59
		4 years	32,000	1.51
		5 years	44,000	1.42
Rhabdomyolysis /myopathy	0.3% ¹⁰⁻¹¹	3 years	58,000	1.77
		4 years	70,000	1.69
		5 years	86,000	1.61

Given alpha=0.05 (two-sided), statistical power = 80%, prevalence of dronedarone in the cohort = 17.1%, baseline event rate = 1.1% for digitalis intoxication, and 0.3% for rhabdomyolysis /myopathy, and right censoring rate = 30%

*Estimated based on the preliminary results of the available LabRx data as of August 31, 2010

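### The 336-event trigger for the final analysis delivers the claimed power at a hazard ratio of 1.5 only if 17.1% is the realised dronedarone share of at-risk time, which the protocol neither states nor checks

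*Protocol*

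**What the plan says.** Section 5 (Study Timelines) expects that the database may lack the power to exclude a hazard ratio of 1.5 until 2014. It plans a yearly check of events, potential participants, patients prescribed both drugs, and the power that follows from the numbers of events and dronedarone users. It then adds a trigger tied to the same hazard ratio of 1.5: "Provided that 336 or more events are captured for any outcome(s) of interest before 2014 which will be sufficient to rule out" that value. Once it is met, the final analysis and report for that outcome begin at once.

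The exposed share behind the calculations is a single constant. Section 3.6 gives it as "17.1% prevalence of dronedarone use in the study population" and labels it the sponsor's prediction. The note under Table 3 gives it as "prevalence of dronedarone in the cohort = 17.1"%. Both places set it beside numbers of participants.

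Section 3.3 defines exposure differently. Concomitant use is "defined as the treatment period during which a patient is on both of the drugs". Reference time starts at the first digoxin or statin fill and stops when dronedarone or amiodarone overlaps. Concomitant time stops when the overlap ends, plus up to 30 days. One patient can contribute episodes to more than one group, and amiodarone co-use is a third group.

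**The concern.** In a Cox model with time-varying exposure, each event carries information of about p(1 − p), where p is the exposed share of those at risk at that moment. A share of patients who use dronedarone at some point is not that quantity. Users' time on digoxin or a statin alone, before and after dronedarone, belongs to the reference group, and observation begins at the US launch, when uptake is near zero. A person-based 17.1% would therefore overstate p.

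The trigger also does not depend on exposure at all. Taken literally, 336 events with very little dronedarone time among them would still start the final analysis. Even if 17.1% was meant as a time share, it is a prediction that the rule never replaces with the observed value.

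At stake is a final safety analysis begun early, on the stated ground that 1.5 can be excluded, when the precision may not be there. The trigger is within reach for digitalis intoxication: the four-year cohort gives 32,000 × 1.1% = 352 events before any censoring.

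**Working it through.** **Inputs.** Two-sided alpha 0.05 and power 80% (Table 3 note: "Given alpha=0.05 (two-sided), statistical power = 80"%); exposed share 0.171 (Section 3.6 and Table 3 note); hazard ratio 1.5 and 336 events (Section 5).

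**Step 1: reproduce 336.** Schoenfeld's formula is events = (1.960 + 0.842)² / [p(1 − p)(ln HR)²].

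- Numerator: 7.849
- p(1 − p) = 0.171 × 0.829 = 0.14176
- (ln 1.5)² = 0.1644
- Events = 7.849 / (0.14176 × 0.1644) = 336.8

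Power at 336 events is 79.9%. Other formulas do not give 336: one-sided Schoenfeld 266, Freedman with unequal groups 261, a Poisson likelihood-ratio approximation 285, and 1:1 groups 191 (Schoenfeld) or 197 (Freedman). So 336 is right for its inputs, and those inputs are two groups with a constant 17.1% exposed.

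Table 3 is consistent with the same constant. A Poisson likelihood-ratio calculation with baseline events N × rate × 0.7 gives 1.59, 1.52, 1.44 for digitalis intoxication (stated 1.59, 1.51, 1.42) and 1.76, 1.69, 1.61 for rhabdomyolysis/myopathy (stated 1.77, 1.69, 1.61).

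**Step 2: express the requirement as information.** D × p(1 − p) must reach 7.849 / 0.1644 = 47.7. At p = 0.171, 336 events give 336 × 0.14176 = 47.6, so the count meets the requirement at that share and falls short at any lower one.

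**Step 3: vary p.** The protocol gives no person-time share, so the lower rows are assumptions. They take 17.1% as a share of patients and suppose that users are exposed for three quarters or half of their at-risk time: 0.171 × 0.75 = 0.128 and 0.171 × 0.5 = 0.0855. Power at 336 events is Φ[√(336 p(1 − p)) × ln 1.5 − 1.960]. The detectable hazard ratio is exp[2.802 / √(336 p(1 − p))].

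| p | p(1 − p) | Power at 336, HR 1.5 | Detectable HR at 336 | Events needed for HR 1.5 |
|---|---|---|---|---|
| 17.1% | 0.1418 | 79.9% | 1.50 | 337 |
| 12.8% | 0.1118 | 70% | 1.58 | about 427 |
| 8.6% | 0.0782 | 55% | 1.73 | 611 |

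**Step 4: rising uptake.** If p climbs linearly from 0 to 17.1% over follow-up with events spread evenly, the mean of p(1 − p) is 0.171/2 − 0.171²/3 = 0.0758. Then 47.7 / 0.0758 is about 630 events, and power at 336 is 53%. Using the overall p of 8.55% instead gives 0.0782, slightly too favourable.

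**Step 5: amiodarone time.** Suppose, as an assumption, that a fraction a of events and time falls in the amiodarone group while 17.1% remains the dronedarone share of all time. The information is then 336 × 0.171 × [1 − 0.171/(1 − a)]. At a = 5% this is 47.1 and at a = 15% it is 45.9, so power falls only to about 79% and 78%. Counting these events is a minor part of the problem.

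**The case against.** The strongest reply is that 17.1% is nowhere defined as ever-use. A prevalence can mean the average share on the drug at a given time, and on that reading, if the prediction comes true, 336 stands. This is correct, and it limits the claim to what the rule fails to guarantee.

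The lower shares are also assumptions, and parts of Section 3.3 keep the exposed share up. Off-drug gaps are not reference time, concomitant time runs up to 30 days past the overlap, and a patient already on dronedarone at cohort entry is exposed from the first day. The table in the working shows sensitivity and does not predict the result.

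The yearly power check helps, because it would bring in observed uptake. But it works from numbers of users and not exposed time, and the 336-event sentence stands as a sufficient condition that does not depend on the check's result. The check softens the point without removing it.

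The harm is bounded too. Table 3 has digitalis intoxication at 1.51 by mid-2013, so the trigger would bring the analysis forward only modestly, and the confidence interval in the report would show the precision achieved.

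A reader might go further and infer three things that the document does not support:

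- **That 336 is miscalculated.** It is not; only the input is in question.
- **That Table 3 is shown to be optimistic.** That follows only if 17.1% is a share of patients. Recomputed cells would also depend on how the 30% censoring entered the calculation, which the protocol does not spell out.
- **That offering the trigger for rhabdomyolysis/myopathy is an error, because 86,000 × 0.3% = 258 is below 336.** The trigger is conditional, Section 5 warns that power may be lacking until 2014, and Table 3 already states 1.61 for that outcome at five years. A trigger that is not expected to fire contradicts nothing.

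**Conclusion.** The point holds in a conditional form. Section 5 treats 336 captured events as enough in themselves, but they give about 80% power at a hazard ratio of 1.5 only if dronedarone-concomitant time makes up 17.1% of the at-risk time. The protocol does not say that 17.1% is such a share, and the trigger does not use the observed one. If 17.1% is a share of patients, or if uptake falls short, the final analysis can start without the stated power: 70% at p = 12.8% and 55% at p = 8.6%, both illustrative. If 17.1% is a realised time share, the count is sound apart from the small loss to amiodarone time. Severity is moderate, because this concerns an input assumption and a trigger that is not tied to exposure, and the yearly check mitigates it in part.

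**What to change.** In Section 5, replace the fixed count with an information rule. The final analysis for an outcome starts when D × p × (1 − p) reaches about 47.7. D is the number of events in dronedarone-concomitant plus reference time, leaving out amiodarone time. p is the observed dronedarone share of that same at-risk time. Because uptake rises after launch, p(1 − p) is better averaged over the event times than computed from one overall p. The share comes from exposure time, so events need not be split between the dronedarone and reference groups to apply the rule. Base the yearly power check on the same quantity. The rule remains approximate because it makes no allowance for covariate adjustment.

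In Section 3.6, state whether 17.1% is a share of patients or of person-time. If it is of patients, restate Table 3 with a person-time share over a range.

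The cost is protocol wording and, in the second case, a recalculated table; no extra data are needed. The downside is that the stated detectable hazard ratios may become less favourable and the trigger may fire later.

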7 TABLES AND FIGURES

Table 1 Distribution of gender, age, and region of patients in the LabRx as of 2008 and in the US general population in 2005

Attributes	LabRx	US Population (2005)*
Male	50%	49%
US Region	Total Lives (%)	Total Lives (%)
Northeast	22%	19%
North Central	30%	22%
South	30%	36%
West	18%	23%
Age Group	Total Lives (%)	Total Lives (%)
00-20	28%	27%
21-39	32%	29%
40-64	34%	32%
65+	6%	12%

*Statistical abstract, US Census

Table 2 Age distribution in AF/AFL Patients in the LabRx (1/1985-3/2008)

Age (yrs)	N	%
18-29	3,705	1.5
30-49	36,089	14.2
50-64	86,431	34.1
>65	127,516	50.3
Total	253,741	100.0

Table 3 Estimated sample size

Outcome	Incidence in literature	Size of cohort*		Hazard Ratio
Digitalis intoxication	1.1% ⁹	3 years	25,000	1.59
		4 years	32,000	1.51
		5 years	44,000	1.42
Rhabdomyolysis /myopathy	0.3% ¹⁰⁻¹¹	3 years	58,000	1.77
		4 years	70,000	1.69
		5 years	86,000	1.61

Given alpha=0.05 (two-sided), statistical power = 80%, prevalence of dronedarone in the cohort = 17.1%, baseline event rate = 1.1% for digitalis intoxication, and 0.3% for rhabdomyolysis /myopathy, and right censoring rate = 30%

*Estimated based on the preliminary results of the available LabRx data as of August 31, 2010

8 APPENDICES

N/A
